subarachnoid haemorrhage other or unspecified and they subsequently died within 30 days (based on the very low rate of mortality from non-aneurysmal SAH) and did not have any additional codes for trauma indicating a non-aneurysmal event.

Data collection - other considerations - central HES ONS data

Last follow-up for each patient will be set as the time at which the HES search was performed, or the patient was unregistered with a GP in the UK or date of death, or the aneurysm was treated, whichever is earliest.

Additionally, we will record

- 1. race
- 2. I10 essential (primary) hypertension
- 3. Z72.0 tobacco use
- 4. F17.2 tobacco dependence

And use these to complete any missing baseline data. Where baseline data and HES conflict, the baseline data will be used. Where neither is available, after assessment for any bias (missing completely at random MCAR, missing at random MAR, missing not at random MNAR) multiple imputation will be used.

Statistical analysis - Aim 1 - PHASES validation

The PHASES study provides the coefficients from their Cox regression model and baseline survival at 5 years that allows the absolute 5-year risk of rupture, to be calculated for all patients who are not censored before 5 years, using age, whether the patients has hypertension, history of SAH, size of aneurysm (3 categories) and location of aneurysm. The time to censoring will be calculated (death or date of HES search or date unregistered from GP practice whichever is first) to ensure 5 years of follow up if rupture has not occurred. Discrimination will be assessed using Harrell's C-index of concordance and Royston and Sauerbrei's D statistic. Calibration will be assessed at the 5 year time point using the method in Royston (2014). These will be used to calculate the number of SAH events per 5 years for each PHASES score (0 to 12+) and expressed as a percentage with 95% confidence interval to compare to the PHASES estimates.

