There are multiple potential causes leading to underestimates of rupture risk. The magnitude of these will be estimated and corrected for. In view that all SAH events will be verified in clinical notes it is not expected that there will be any significant overestimation and consequently correction. Events may be missed due to migration. Any patients noted at time of baseline data collection to have emigrated will have this recorded and this will be used for censoring. Additionally, HES data will reveal any patients who have unregistered with their GP for emigration which will be used as a censoring event. Unfortunately, it is anticipated that not all patients will unregister on departure from the UK and therefore the observed emigration rate (that from the baseline data collection and HES data) will be subtracted from average national migration figures and this applied to the data.

Events may be missed due to miscoding. Aneurysmal SAH miscoded as:

1. Cerebral infarction (63.0-63.9 & I64.X)

Will be identified at one or more test sites by review of clinical notes to estimate any under-estimates due to miscoding and these estimates applied to the whole cohort.

In the event there are high rates of failed verification for the codes:

- 1. Intracerebral haemorrhage (including intraventricular haemorrhage (I61.0-61.9)
- 2. Subarachnoid haemorrhage (other and unspecified) (I60.8-60.9)
- 3. Non-traumatic subdural haemorrhage (I62.00-I62.02)
- 4. Traumatic subarachnoid haemorrhage (S06.6X0, S06.6X9A, S06.6X9, S06.6X8A)
- 5. I46.1 sudden cardiac death R98 unattended death
- 6. R96 other sudden death cause unknown
- 7. R98 unattended death

at some centres, then error estimates may be applied to the data from centres with robust code verification.

Additionally, at baseline data collection, any subsequent SAH events observed in the local notes will be recorded with their date, or date of last follow up. The SAH events observed during this follow up period will be compared to that for the similar period using HES data (after applying the above corrections), and the total risk estimates adjusted for any differences between these to give final 5 year risk estimates.

Discrimination will be assessed with the C statistic but is expected to be poor due to low event rates and therefore will be compared to the original PHASES data. Calibration will be assessed with calibration plots and Hosmer-Lemeshow tests.

Statistical analysis – Aim 2 - Additional prognostic factors

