A new risk prediction model for rupture will be developed using the total data set, including the additional possible risk factors. The Cox regression model will be used for risk of rupture. The absolute risks can be estimated at relevant time intervals, 2, 5 and 10 years. Numbers of missing values will be summarised for each factor. Multiple imputation will be used to replace missing values. Discrimination of the final model will be assessed with the Harrell's c-statistic. Internal validity will be assessed by bootstrap resampling.

Additionally, the following sensitivity analyses will be performed:

In view that a significant number of aneurysms are anticipated to have grown and subsequently treated on follow up, any cases noted to have undergone treatment for aneurysm growth will be included in a model predicting the risk of rupture or treatment for aneurysm growth. In view that it is anticipated that a number of unexplained deaths will be captured where it will not be possible to resolve if the cause was SAH or not, a model predicting aneurysm rupture or unexplained or unattended death (R 96 and 98) will be built.

Statistical analysis - Aim 3 - Long term rupture rates

It is anticipated that initially follow up times will range from months to 15 years. This will be insufficient to definitively answer what the long term risks posed by aneurysms are. However, a model will be built including a term for new diagnosis vs known diagnosis. This will establish if rupture rates are similar between patients with new and prior diagnoses.

All patients, including those who underwent aneurysm occlusion, will be included in time-to-event analysis which will cover the whole duration of available follow-up. This will include Kaplan-Meier and proportional hazards models for univariate and multivariate survival curve fitting. A cumulative Hazard plot will be used to assess if rupture risk is constant or varies with time from diagnosis.

Longer term, HES searches will be repeated periodically using unique HES identifiers generated by DARS at the first HES search. These searches will identify any late events of SAH due to aneurysm rupture and models will be built to predict true long-term risk.

Data management

Patient confidentiality

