7.2 Sampling

7.2.1 Size of sample

Sample Size

There are no accepted methods for power calculation for validation studies of prognostic models. Therefore, usually the rule of thumb to have ten events for every covariate tested is applied.

For Aim 1, 6 covariates will be tested suggesting at least 60 SAHs will need to be captured. ISUIA recorded 51 ruptures in 1692 patients over 4.1 years. Sixty events may therefore be expected in 1,990 patients with 8,161 years of follow up.

For Aim 2, 120 events will need to be observed to account for the 6 additional commonly occurring covariates which would be expected in 3,981 patients with 16,332 years of follow up.

For autosomal dominant polycystic kidney disease (ADPKD) which has a low incidence, larger numbers of patients will be needed. Ten events in ADPKD are expected in 1360 patient years of follow up assuming the risk of SAH is not elevated and similar to the general population. However, 16,332 years follow up would only yield 195 years in patients with ADPKD (based on a population study which found 53/4436 IAs had ADPKD (Nurmonen 2017) and consistent with pilot data where 11/1025 cases examined to date had ADPKD). Therefore 113,905 years of follow up would be required to capture 10 ruptures amongst 1,340 years follow up in ADPKD patients. This would equate to 22,781 patients with 5 years of follow up (or applying the slightly looser rule of 5 events per prognostic factor this would require 56,952 years of follow up with 11,391 patients).

In a local pilot 1,415 cases were identified over 14 years in a population of 3 million with an anticipated 6,000 years of follow up. Extrapolating to England, Wales and Scotland 31,130 patients with 132,200 years follow up are available - well in excess of the target of 8,161 to validate PHASES in the general population, as well as the 16,332 to test the additional variables, but only just sufficient to answer the role of rarer predictors such as ADPKD. For reference PHASES was based on 29,166 years of patient follow up. Therefore, all cases that can be identified in England and Wales will be sought up to a maximum of 22,781.

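### Aim 1 calibration keeps early ruptures but drops patients censored before 5 years, so a correctly calibrated PHASES score will look too low and the Hosmer-Lemeshow test will usually reject it

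*Protocol*

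**What the plan says.** All Aim 1 statements are in protocol section 5, under the heading for PHASES validation.

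- The model is external and fixed: "The PHASES study provides the coefficients from their Cox regression model and baseline survival at 5 years".
- The 5-year absolute risk is "to be calculated for all patients who are not censored before 5 years".
- Time to censoring is worked out "to ensure 5 years of follow up if rupture has not occurred".
- A first calibration statement reads "Calibration will be assessed at the 5 year time point using the method in Royston (2014". The reference list describes that source as a set of tools for checking a Cox model in external validation.
- The last sentence of the same subsection reads "Calibration will be assessed with calibration plots and Hosmer-Lemeshow tests". It gives no number of groups, degrees of freedom or treatment of censored patients, and no order of priority between the two calibration statements.

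On follow-up, the Aim 3 text says "It is anticipated that initially follow up times will range from months to 15 years", and section 7.2.1 says "Extrapolating to England, Wales and Scotland 31,130 patients with 132,200 years follow up are available".

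**The concern.** A Hosmer-Lemeshow test compares counts of events with sums of predicted probabilities, so every patient analysed must have a known status at 5 years. With mean follow-up below 5 years, many patients will not.

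The Aim 1 text settles this by selection, and the selection depends on the outcome. A patient who ruptures at year 3 is kept. A patient who leaves follow-up at year 3 without rupture is removed. The numerator keeps every observed rupture while the denominator loses most of the rupture-free patients with short follow-up, so observed risk is pushed above its true value.

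At stake is the main question of Aim 1: whether the PHASES 5-year risks hold in UK patients. Section 1 says 24 of 30 UK units use the score and that it has not been validated in this population. A calibrated score could be reported as markedly underpredicting. Nothing else in the plan would pull the estimate back, because section 5 plans corrections only for underestimation and expects no material overestimation. The same selection would inflate the calibration plot and the percentages for each score if they use the same patients.

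**Working it through.** **1. The plan's own figures.** From "ISUIA recorded 51 ruptures in 1692 patients over 4.1 years" (section 7.2.1):

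- Rate = 51 / (1,692 × 4.1) = 0.735% per year.
- Sixty events: 60 × 1,692 / 51 = 1,990.6 patients, and × 4.1 = 8,161 years. The stated 1,990 and 8,161 reproduce.
- Mean follow-up: 132,200 / 31,130 = 4.25 years. The pilot gives 6,000 / 1,415 = 4.24 years. Both are below the 5-year horizon.

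**2. The bias by hand.** Assume one common rupture rate λ = 0.00735 per year, and censoring uniform on 0 to 8.5 years (mean 4.25) and independent of risk.

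- True and predicted 5-year risk: 1 − exp(−5λ) = 0.0361.
- Share of the cohort with a rupture observed by 5 years: ∫₀⁵ λ exp(−λt)(1 − t/8.5) dt = 0.0255.
- Share rupture-free and still followed at 5 years: exp(−5λ) × (1 − 5/8.5) = 0.9639 × 0.4118 = 0.3969.
- Share kept by the Aim 1 rule: 0.0255 + 0.3969 = 0.4224.
- Observed risk among those kept: 0.0255 / 0.4224 = 0.0605.
- Observed/expected: 0.0605 / 0.0361 = 1.68, although the score is exactly right.

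**3. The test by simulation.** Outcomes were drawn from the predicted risks, so calibration is perfect. Assumptions not in the documents: 10 risk groups, nominal 5%, exponential rupture times, lognormal risk with log-SD 0.8, and independent censoring. Heavy censoring was either uniform on 0 to 8.5 years or exponential cut at 15 years, both with a mean near 4.25 years. Mild censoring was uniform on 2 to 15 years. There were 1,000 runs per cell (300 at N = 22,781). Rejection rates under the Aim 1 rule:

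| | Heavy, 10 df | Heavy, 8 df | Mild, 10 df | Mild, 8 df |
|---|---|---|---|---|
| N = 1,990 | 79–83% | 87–89% | 24% | 36% |
| N = 3,981 | 96–97% | 98–99% | 33% | 45% |
| N = 22,781 | 100% | 100% | 96% | 98–99% |

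Observed/expected was 1.64–1.75 with 34–42% of patients kept (heavy), and 1.19–1.20 with about 78% kept (mild). With uniform heavy censoring at N = 22,781, changing the rate to 1.4% per year (the figure in section 1) gave a ratio of 1.59, and changing the log-SD to 0.4 gave 1.67. Rejection stayed at 100% in both cases.

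**4. Separating the causes.** When every patient's 5-year status is known, the same test on 10 df rejects 4–7% of the time, close to nominal. On 8 df, the reference for a model fitted in the same data, it rejects 9–15%; the exact value is P(χ²₁₀ > 15.51) = 11.5%. The step from there to 79–100% under heavy censoring comes from the patient selection.

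**5. Effect of the repair.** Using all patients, the Kaplan-Meier 5-year risk divided by mean predicted risk averages about 1.00 in the same set-up, as it must when censoring is independent. A grouped test comparing Kaplan-Meier risk with predicted risk (Greenwood variance, 10 df) rejects 7–10% at N = 22,781. It remains liberal at N = 1,990 (12–20%), where events per group are few.

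**The case against.** The strongest reply is that the test is not at fault. Given the patients that the Aim 1 text selects, observed risk really is inflated and a rejection reports that correctly. A calibration plot or a crude ratio on the same patients would be equally wrong. This stands, and it is why the restriction is treated here as the main cause.

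A second reply is that the test is redundant. No decision rests on its p-value, and the plan also has calibration plots, the cited method for Cox models and percentages by score with confidence intervals. This stands in part. Those outputs give size and direction, but the Aim 1 text as written limits the 5-year risk calculation that they rest on to the same patients.

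Stronger readings that a reader might infer are not supported:

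- **The test is invalid on external data because its reference distribution assumes a model fitted in those data.** The protocol states no degrees of freedom, and with 10 the test is close to nominal when outcomes are complete. Degrees of freedom may properly be left to the SAP.
- **The test could pass a score that underpredicts UK risk.** That requires counting early-censored patients as non-ruptures, which the protocol does not say. Under the written rule the bias runs the other way.
- **No such test can be computed once censoring is respected.** Grouped versions for survival data exist.
- **The two calibration statements are incompatible.** They are two assessments with no stated priority. The paper behind the first is not in the documents beyond its title.

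**Conclusion.** The point holds in this form: followed as written, the Aim 1 calibration analysis overstates observed rupture risk and will tend to declare a correct PHASES score miscalibrated. The overstatement is about 64–75% if follow-up averages about 4.25 years in the patterns tried, and about 20% with mild censoring. At the planned maximum of 22,781 patients, rejection is nearly certain (96–100%) whether or not the score is calibrated.

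The direction follows from the selection rule and did not change in any setting tried. The exact rates depend on the assumed risk spread, censoring pattern, number of groups and significance level. The documents give the mean and range of follow-up, not its distribution. Informative censoring was not examined.

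**What to change.** 1. In the Aim 1 text of section 5, replace the restriction to patients not censored before 5 years with all eligible patients, censored at last follow-up. Apply the fixed PHASES coefficients and 5-year baseline survival to each of them.
2. In the closing calibration sentence, delete the Hosmer-Lemeshow tests. If a test is wanted, name a grouped one that allows for censoring and treats the coefficients as fixed.
3. Report the 5-year observed/expected ratio beside the calibration plot. Take observed risk from Kaplan-Meier or cumulative incidence, chosen in advance, and divide it by mean predicted risk. Report the calibration slope as well, each with a 95% confidence interval, and base the Aim 1 calibration conclusion on these.
4. Obtain the percentages for each PHASES score from the same full set of patients.

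The first change is the essential one; the second without the first leaves the bias in place. The cost is a few sentences, slightly more analysis work and the loss of a familiar p-value. No new data are needed.

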We therefore organised a workgroup to discuss UIA research (advertised via the support group Facebook page) where it was confirmed that better decision making on aneurysm treatment is the main concern for patients, but patients do not want to their management to be randomised and therefore an RCT is unlikely to succeed. Consequently, a better understanding of the natural history of UIA, was deemed the top priority and that long term, ideally lifetime risks, are what is relevant to patients.

Since COVID it has not been possible to run our focus groups face to face. Therefore, to specifically evaluate the acceptability of the study design and its proportionality to the problem, over the course of 2020 we have asked a series of patients seen in outpatients with unruptured aneurysms their views. All patients strongly supported a study of the natural history of UIA. The overwhelming majority view the need to better define the aneurysm rupture risk outweighs the risks posed by use of patient identifiable data in this study. Although some declined participation in imaging or interventional studies, all confirmed they would be happy for their records to be searched for a natural history study, without full informed consent, as we propose.

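### Absolute rupture risks for Aims 2 and 3 come from Cox and Kaplan-Meier methods that end follow-up at death, so they are net risks and not the probability of rupture

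*Protocol*

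**What the plan says.** All the relevant text is in protocol section 5.

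- **End of follow-up** (central HES ONS data, other considerations). Last follow-up is the HES search date or GP de-registration, "or date of death, or the aneurysm was treated, whichever is earliest".
- **Aim 1.** Death is grouped with the administrative end dates: "The time to censoring will be calculated (death or date of HES search or date unregistered from GP practice whichever is first".
- **Aim 2.** "The Cox regression model will be used for risk of rupture", and then "The absolute risks can be estimated at relevant time intervals, 2, 5 and 10 years".
- **Aim 3.** The time-to-event analysis covers all available follow-up: "This will include Kaplan-Meier and proportional hazards models for univariate and multivariate survival curve fitting". A cumulative hazard plot is added to judge whether risk changes with time. On duration: "It is anticipated that initially follow up times will range from months to 15 years". After later repeat searches, "models will be built to predict true long-term risk".

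No cumulative incidence function, Fine-Gray model or other competing-event method is named. Death enters an outcome only in an Aim 2 sensitivity model that pools unexplained or unattended death with rupture. That model addresses ruptures that may have been missed. It does not treat death from other causes as a competing event.

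**The concern.** Censoring a patient assumes that the patient could still have the event later, at the same rate as similar patients who remain under observation. Someone who has died of another cause cannot rupture. If death is censored, one minus the Kaplan-Meier estimate, or one minus the survival predicted by a Cox model, answers a hypothetical question: how many would rupture if no other death could occur? The protocol does not declare that quantity as its target. It promises absolute risks, which a reader will take as the chance that a patient with these features has a rupture within the stated time.

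The difference grows with the horizon and with mortality. It therefore matters most for what Aims 2 and 3 add to PHASES, namely risks at 10 years and over follow-up of up to 15 years. The Aim 1 text expects no material overestimation because events are checked against notes. That covers falsely counted ruptures, but not an excess that arises from the estimator.

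**Working it through.** **Inputs.** The rupture rate comes from the sample size section (7.2.1): 51 ruptures in 1,692 patients over 4.1 years.

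r = 51 / (1,692 × 4.1) = 51 / 6,937.2 = 0.00735 per year (0.735%).

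**Check against the plan's own figures.** 60 / r = 8,161 years, as stated for Aim 1. 120 / r = 16,323 years, against 16,332 stated for Aim 2; the difference has no bearing here. The protocol gives no 10-year risk to reproduce.

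**Assumption.** The protocol gives no mean age and no death rate. Other-cause mortality m is therefore assumed, at 1%, 2%, 5% and 8% per year, constant over time.

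**Formulas.**
- Net risk (death censored): 1 − exp(−r·t).
- Cumulative incidence (death competing): r / (r + m) × [1 − exp(−(r + m)·t)].

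**Worked case, t = 10, m = 0.05.** Net risk = 1 − exp(−0.0735) = 7.09%. Cumulative incidence = 0.00735 / 0.05735 × [1 − exp(−0.5735)] = 0.1282 × 0.4365 = 5.6%. The ratio is 1.27.

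**Results at r = 0.735% per year** (relative excess of net risk in brackets):

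| Horizon | Net risk | m = 1% | m = 2% | m = 5% | m = 8% |
|---|---|---|---|---|---|
| 2 years | 1.46% | 1.45% (1%) | 1.43% (2%) | 1.39% (5%) | 1.35% (8%) |
| 5 years | 3.61% | 3.52% (2.5%) | 3.44% (5%) | 3.20% (13%) | 2.98% (21%) |
| 10 years | 7.09% | 6.75% (5%) | 6.43% (10%) | 5.59% (27%) | 4.90% (45%) |
| 15 years | 10.44% | 9.71% (8%) | 9.05% (15%) | 7.40% (41%) | 6.15% (70%) |

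**Sensitivity to the rupture rate.** The protocol also quotes about 1% per year (section 3) and 1.4% per year (section 1). The relative excess barely moves: at 10 years with m = 5% it is 27% and 26%.

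**Sensitivity to rising mortality.** Let other-cause mortality start at 0.5%, 1% or 2% per year and double every 8 years (assumed). The cumulative incidence is then the integral from 0 to t of r·exp(−r·s − H(s)), where H(s) is the cumulative other-cause hazard. At r = 0.735% the excess is 3%, 7% and 14% at 10 years, and 6%, 12% and 25% at 15 years.

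**The case against.** The strongest defence is that, for Aim 2, the error is partly inferred. The sentence that explicitly calls death censoring belongs to Aim 1, where comparability with PHASES justifies it. Ending follow-up at death is common to every survival analysis, including a competing-risks one. The Aim 2 text does not say how hazards become risks, and a statistical analysis plan could. Net risk is also a legitimate natural-history quantity.

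Part of this stands. The Cox hazard ratios, the comparison of new with known diagnoses and the cumulative hazard plot are all valid cause-specific quantities with death censored. Only the conversion to absolute risk is in question. There the protocol is not merely silent. It names a Cox model for rupture as the source of absolute risks and Kaplan-Meier for Aim 3, and the usual output of both is the net risk. It does not declare net risk as the target.

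A reader might go further in three ways that the document does not support.

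- **That the reported risks will be too high overall.** Section 5 itself describes ruptures missed through migration and miscoding. Follow-up also stops at treatment, which could lower the estimate if higher-risk aneurysms are the ones treated. The net bias is not established.
- **That lifetime or 30-year risks will be badly wrong.** The patient involvement section (8.4) does say that "long term, ideally lifetime risks, are what is relevant to patients", but the specified horizons are 2, 5 and 10 years. Aim 3 concedes that the initial follow-up cannot settle long-term risk, and the methods for later models are not given.
- **That the excess is large because the cohort is elderly, and would distort treatment decisions.** Eligibility is 18 years or older with no age distribution given, and no effect on decisions can be derived from the document.

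**Conclusion.** The point holds in a limited form. The methods named for Aims 2 and 3 lead naturally to a net risk that exceeds the probability of rupture whenever other-cause deaths occur. The direction of this component is certain. Its size is not, because mortality is assumed throughout. Across 1% to 8% per year, the relative excess is about 1-8% at 2 years, 2.5-21% at 5 years, 5-45% at 10 years and 8-70% at 15 years. The upper end needs a constant 8% per year, under which only exp(−0.8) = 45% of patients would escape other-cause death for 10 years. With low mortality the effect is small at 2 and 5 years and modest at 10. The change should be made, but the point does not invalidate the study or its hazard ratios.

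**What to change.** In the Aim 2 and Aim 3 analysis text of section 5:

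- Keep the Cox model for cause-specific hazard ratios, and keep the cumulative hazard plot.
- Report absolute risks as cumulative incidence of rupture with non-SAH death as a competing event, chiefly at 10 years and beyond. Use either a Cox model for rupture combined with one for non-SAH death, or a Fine-Gray model.
- Show Aalen-Johansen curves in place of one minus Kaplan-Meier.
- Keep the death-censored risk for Aim 1, labelled as a net risk, so that the comparison with PHASES stays like for like.

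The cost is a few lines of text. Date and cause of death are already collected locally, and ONS linkage is planned, so no new data are needed. The drawback is that two risk scales will be reported and must be clearly labelled wherever they appear.
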